2. To test intervention effects on the secondary outcomes of reduced internalized HIV stigma, increased HIV serostatus disclosure, and increased viral load suppression among participating PLWH, and PrEP uptake among their social network members.
3. To examine whether increased HIV prevention advocacy by PLWH mediates intervention effects on their social network members’ increased HIV testing and condom use, and whether increased HIV disclosure by PLWH mediates intervention effects on social network members’ reduced HIV stigma.
4. To conduct a cost-effectiveness analysis of the intervention.

We will recruit 210 PLWH, randomizing 105 to the intervention and 105 to a no-intervention control condition. Each PLWH will be asked to recruit social network members (up to 4, with expected average of 3.5 network members per participant) to complete assessments (736 total network members, 368/arm), and test intervention effects on social networks. All participants will complete surveys at baseline, and 6-, 12-, and 18-months post-baseline. The cost-effectiveness analysis will inform policymakers about whether *Game Changers* is a feasible intervention in which to invest.

Our approach is particularly timely in the era of biomedical interventions, which require widespread penetration of effective HIV prevention and care messaging into communities. Positioning PLWH as central to the solution for controlling (vs. causing) the HIV epidemic has the potential to reduce HIV stigma and improve prevention outcomes at the individual, household, and network levels. Consistent with theories of social diffusion, cognitive consistency, and social influence, studies show peer advocacy interventions reduce HIV risk in advocates themselves.⁶⁻¹⁰ However, with the exception of our pilot work, we are unaware of studies of the effects of prevention advocacy by PLWH with family, friends and community members. If successful, the intervention will be a significant innovation for the field, as it targets advocacy to all types of social network members rather than specific peer or risk groups, and uses social network information to strategically target advocacy.

SIGNIFICANCE

HIV Prevalence Remains High in Uganda

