Aims 1-3. Primary analyses will use a standard intent-to-treat approach, applying generalized mixed models (linear for continuous outcomes; logistic for binary outcomes) to the repeated-measures data to examine how intervention effects change over time, using an indicator for study arm, timepoint (baseline vs. follow-up), and timepoint by arm interaction to indicate whether change differs between arms. Our statistical methods will be consistent with advances in the analysis of personal network research,^{66, 135-137} accounting for any correlation among participants in the same intervention group sessions, and among alters referred by the same PLWH (ego), by adjusting standard errors for statistical inference tests with a sandwich estimator as implemented in SAS v 9.4.^{96, 138-141} We will use imputation for item nonresponse and account for non-random dropouts using logistic regressions that assign weights to retained participants that are inversely proportionate to the predicted probability of the participant being retained; if dropout is random, analyses will incorporate design effects. In follow-up analyses, we will explore interactions between each potential moderator and arm, including sex (of ego and/or alter, and concordance between the two) to examine if these variables moderate the intervention effects. If interactions with categorical moderators are significant, we will conduct post-hoc simple main effects t-tests with Bonferroni corrections. For continuous moderators,¹⁴² we will graph significant interactions at low and high levels of each score (± 1 SD). We will conduct post-hoc simple main effects t-tests with Bonferroni correction by comparing differences between discrete points on the regression lines. If *Game Changers* shows significant effects on hypothesized mediators (Aim 3), to test mediation we will compare: (a) Aim 1 models, adding baseline measures of mediator(s); and (b) the same models as in (a), adding post-intervention measures of mediator(s).¹⁴³ We will examine whether including post-intervention mediator(s) in (b)

decreases the coefficient for intervention effects on outcomes relative to the corresponding coefficient from (a). We will use a bootstrapping approach to test whether mediators account for effects.^{144, 145}

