Statistical Power. We calculated power for alter reports of condomless sex at month 18. Based on the pilot, we assume 65% of control alters will report condomless sex at month 18. Starting with 736 alters, and assuming ~15% attrition by month 18 (which is conservative, based on 98% alter retention over 8 months in the pilot, and <10% attrition over 12 months in our other studies in Uganda), we will have 625 alters; accounting for within-ego clustering gives us an effective sample size of 612 for ICC=.01 or 568 for ICC=.05. For ICC=.01, we will have .80 power to detect a group difference of 10.3% (i.e., an intervention rate of 54.7%), and for ICC=.05, we will have power to detect a 10.7% group difference. These differences represent small effect sizes (Cohen's $d = .23\text{--}.24$). For PLWH index participants, using pilot data, we estimate the ICCs of our secondary outcomes to be small-to-moderate (0-.16), and assume 15% attribution and 7 intervention groups (either Game Changers or attention control), with an average cluster size of 12.9 (90 intervention participants/7 groups).^{96, 140, 141} After accounting for within-group correlations, we will have 80% power to detect medium to large differences (.41-.58 SD, based on the outcome) between the study arms at follow-up.

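### Mediation is estimated only if the arm effect on the mediator is significant, so Aim 3 may get no estimate, and the estimates it does get are biased upward on average

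*Combined protocol and SAP*

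**What the plan says.** Aim 3 in the Specific Aims names three mediator-outcome pairs: advocacy by PLWH for network members' HIV testing, the same for their condom use, and "whether increased HIV disclosure by PLWH mediates intervention effects on social network members’ reduced HIV stigma". No condition is attached.

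The Statistical Analysis section (Aims 1-3) adds one. If the intervention shows "significant effects on hypothesized mediators (Aim 3), to test mediation we will compare" two models: (a) the Aim 1 model with the baseline mediator added, and (b) the same model with the post-intervention mediator added as well. The quantity examined is whether (b) "decreases the coefficient for intervention effects on outcomes relative to the corresponding coefficient from (a"). Inference follows: "We will use a bootstrapping approach to test whether mediators account for effects". The models are "linear for continuous outcomes; logistic for binary outcomes".

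The section gives no significance level for the condition, no correction for selecting on it, and no statement of what is estimated if it fails.

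Statistical Power gives the only precision figure at PLWH level: "we will have 80% power to detect medium to large differences (.41-.58 SD, based on the outcome"). It is stated for the PLWH secondary outcomes. By Aim 2 these include serostatus disclosure but not prevention advocacy.

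**The concern.** Two consequences follow from the condition.

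- **Missing answer.** A mediator whose arm effect narrowly misses significance gets no indirect-effect estimate and no interval. Aim 3 is then unanswered for that mediator, although the data to estimate it exist.
- **Selected answer.** An arm-to-mediator estimate is more likely to pass when it lies above its true value. The indirect effect combines that path with the mediator-to-outcome path, so it carries the same selection.

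What is at stake is how Aim 3 is read: how much of the effect on network members runs through advocacy and disclosure. No primary outcome analysis is affected.

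**Working it through.** **Inputs.** About 90 PLWH retained per arm (the plan's 90 intervention participants in 7 groups of 12.9 on average; 1:1 allocation gives the same number of controls). The ICC range is from the plan: "we estimate the ICCs of our secondary outcomes to be small-to-moderate (0-.16"). Two-sided alpha of .05 is assumed, because none is stated. Clustering is taken in the intervention arm only.

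**1. Reproduce the plan's figure.** Detectable difference = (1.960 + 0.842) × sqrt([1 + (12.9 − 1) × ICC]/90 + 1/90).

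- ICC 0: 2.802 × sqrt(2/90) = 2.802 × 0.1491 = 0.418 SD (plan: .41).
- ICC .16: 1 + 11.9 × .16 = 2.904; 2.802 × sqrt(3.904/90) = 2.802 × 0.2083 = 0.583 SD (plan: .58).

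Both ends reproduce.

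**2. Chance of no estimate.** This is 1 minus the power of the mediator test. At the detectable difference it is 20% per mediator. The plan does not state the true effect, so a smaller value is shown as an assumption. At .30 SD:

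- ICC 0: power = Φ(.30/.1491 − 1.96) = Φ(0.05) = .52, so 48% no estimate.
- ICC .16: power = Φ(.30/.2083 − 1.96) = Φ(−0.52) = .30, so 70% no estimate.

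**3. Average overstatement once the condition is met.** Let θ be the true effect divided by its standard error. Ignoring the negligible opposite tail, power = Φ(θ − 1.96), and the mean significant estimate divided by the truth is 1 + φ(1.96 − θ)/(θ × power). At 80% power, θ = 2.802 and the ratio is 1 + 0.280/(2.802 × 0.80) = 1.125.

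| Power of mediator test | θ | Mean estimate / truth |
|---|---|---|
| .50 | 1.960 | 1.41 |
| .65 | 2.345 | 1.24 |
| .80 | 2.802 | 1.125 |
| .90 | 3.242 | 1.06 |
| .95 | 3.605 | 1.03 |
| .99 | 4.286 | 1.006 |

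At 80% power the share of significant estimates above the truth is .50/.80 = 62.5%. The other 37.5% are not above it.

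**4. The indirect effect itself.** A simulation of the product of the two paths (90 per arm, ICC 0, linear model, assumed mediator-to-outcome slope 0.3, 10,000 runs) gives:

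| True arm effect on mediator (SD) | True indirect effect | Mean, no condition | Mean, condition met | Ratio to truth |
|---|---|---|---|---|
| 0.20 | 0.060 | 0.060 | 0.114 | 1.90 |
| 0.30 | 0.090 | 0.090 | 0.124 | 1.38 |
| 0.42 | 0.125 | 0.124 | 0.140 | 1.12 |
| 0.60 | 0.180 | 0.181 | 0.183 | 1.02 |
| 0.80 | 0.240 | 0.238 | 0.239 | 0.99 |

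Without the condition the mean matches the truth. With it, the inflation follows step 3. At 0.42 SD, 57% of the selected indirect effects exceeded the truth. With a true mediator effect of zero, both paths were jointly significant in 4.9% of runs, so the condition does not raise the false-positive rate.

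**The case against.** The strongest reply is that the bias may be small, may be offset, and concerns a deliberate and referenced stepwise method.

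- **Pilot effects suggest decent power.** Scaling the pilot z-values by sqrt(180/95) = 1.38 (same true effects assumed, group clustering ignored): advocacy at p = .017 gives 2.39 × 1.38 = 3.29, power about .91, overstatement about 6%. Proportion of network members disclosed to, at p = .05, gives 1.96 × 1.38 = 2.70, power about .77, overstatement about 15%. This stands as a reason for modest size. Pilot estimates may themselves be high, and clustering lowers the power.
- **Repeated measures help.** The planned model uses change over time. With three equally correlated follow-ups averaged against baseline, the variance factor is (1 + 2ρ)/3 + 1 − 2ρ, which is .93, .67 and .40 at ρ = .3, .5 and .7. At an assumed .30 SD and ICC 0, the overstatement falls from 38% to 35%, 21% and 7%. Mediators recorded for each PLWH-network member pair could also change the precision. Both points stand; the plan gives no correlation with which to settle them.
- **Other biases run the other way.** In logistic models the drop in the arm coefficient falls short of the product of paths, because odds ratios are non-collapsible. Simulated ratios were .90 and .74 at assumed slopes of 0.5 and 1.0 log-odds per SD, or 1.01 and .83 after the 1.125 factor. The advocacy scale's reliability of .87 would bring 1.125 to roughly 1.125 × .87 = .98. So the net direction for a given estimate is not fixed. But an uncontrolled bias in the other direction is no reason to keep an avoidable one, and it does not restore an estimate that was never made.
- **The arm effect on the mediator is still seen.** Disclosure is an Aim 2 outcome, and applying the condition requires the advocacy effect to be estimated. Their intervals would show imprecision in that path. They do not give the indirect effect that Aim 3 asks about.

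A reader might infer that every reported indirect effect will be overstated, or that the mediation test's false-positive rate is inflated. Neither is supported: 37.5% of significant arm-to-mediator estimates do not exceed the truth at 80% power, and the joint false-positive rate was 4.9%.

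**Conclusion.** The point holds as one about estimation and reporting, and it is minor. The condition leaves an unconditional aim without an answer in 20% of cases per mediator at the plan's own detectable difference, more often if the true effect is smaller. When it is met, it biases the arm-to-mediator path upward on average: about 12-13% at 80% power, about 40% at 50%, 3% or less at 95% and above. The indirect effect is inflated similarly in a linear model.

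These sizes rest on two-sided .05, about 90 PLWH per arm and a single cross-sectional comparison. The .30 SD case is an assumption. The 80% power figure applies to PLWH secondary outcomes, including disclosure; for advocacy, the mediator in two of the three pairs, the plan gives no power, so the size there is unknown.

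**What to change.** In Statistical Analysis, Aims 1-3, delete the clause that makes the mediation comparison depend on a significant mediator effect. State instead that, for each mediator-outcome pair named in Aim 3, the indirect effect will be estimated and reported with its bootstrap confidence interval, whatever the p-value of the arm effect on the mediator.

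No new data, sample size or method is needed, since the bootstrap is already planned. The cost is a few more estimates to report, some with wide intervals.

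### On its most natural reading, Aim 3's drop-in-coefficient rule shows almost no mediation even when mediation is complete

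*Combined protocol and SAP*

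**What the plan says.** Aim 3 (Specific Aims) asks, among other things, whether "increased HIV prevention advocacy by PLWH mediates intervention effects on their social network members" in HIV testing and condom use. Measurement is repeated: "All participants will complete surveys at baseline, and 6-, 12-, and 18-months post-baseline".

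The analysis is in Statistical Analysis, Aims 1-3. The Aim 1 models are fitted by "applying generalized mixed models (linear for continuous outcomes; logistic for binary outcomes) to the repeated-measures data", "using an indicator for study arm, timepoint (baseline vs. follow-up), and timepoint by arm interaction to indicate whether change differs between arms". The interaction is the only term that the text ties to the intervention effect.

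Mediation is tested only if the intervention significantly affects the mediator. The two models compared are given as "a) Aim 1 models, adding baseline measures of mediator(s); and (b) the same models as in (a), adding post-intervention measures of mediator(s"). The criterion is whether model (b) "decreases the coefficient for intervention effects on outcomes relative to the corresponding coefficient from (a"). The next sentence adds: "We will use a bootstrapping approach to test whether mediators account for effects".

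The text does not say what value the post-intervention mediator takes on baseline rows, whether any mediator is crossed with timepoint, which coefficient the mediation sentence means, or which statistic is bootstrapped.

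**The concern.** The rule compares a treatment coefficient before and after adjustment for the mediator. That works when the coefficient is a between-person difference at follow-up. Here it is a difference in within-person change, and a covariate with one value per person shifts all of that person's rows, baseline included, by the same amount. Such a covariate has nothing to say about change.

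Aim 3 tests the causal path in the protocol's conceptual model. A rule that hardly responds to mediation could lead the team to report that advocacy or disclosure does not explain an effect that it does explain.

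**Working it through.** The plan gives no mediation figure to reproduce. The check is algebra, then simulation.

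**1. Algebra, linear model.** Let A be arm, T = 0 at baseline and 1 at follow-up, M0 and M1 the PLWH's baseline and post-intervention mediator, u the alter's random intercept, and k the number of follow-up visits (here 3).

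Model (b): Y = b0 + b1·A + b2·T + b3·A·T + g0·M0 + g1·M1 + u + e

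Mean follow-up minus baseline, per alter: b2 + b3·A + error. The terms g0·M0, g1·M1 and u cancel. With complete data, the estimate of b3 is the arm difference in mean change, with or without M1. The (a)-to-(b) drop is exactly zero, whatever share is mediated.

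**2. Where the mediation goes.** Suppose mediation is complete: Y depends on the current mediator with slope s, and arm shifts M1 by d, so the total effect is s·d. The coefficients of person-constant covariates come from person means, in which M1 has weight k/(k+1). Hence in (b):
- mediator slope g1 = s·k/(k+1);
- arm main effect b1 = -s·d·k/(k+1), a spurious baseline difference;
- follow-up contrast b1 + b3 = s·d/(k+1).

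With k = 3 the contrast falls by 75% rather than 100%, and the slope is 75% of its true value. With a single follow-up both figures are 50%.

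**3. Simulation under 100% mediation.**
- From the documents: 210 PLWH; one baseline and three follow-up rows; about 15% attrition; 65% vs 54.7% condomless sex, giving a log odds ratio of ln(0.547/0.453) - ln(0.65/0.35) = 0.189 - 0.619 = -0.43.
- Assumed, because the documents do not give them: arm effect on the mediator 0.25, 0.5 or 1.0 SD; baseline-to-post mediator correlation 0.5; alter random-intercept SD 1.0 (linear), 0.5 or 1.5 (logistic).

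Timepoint-by-arm coefficient:

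| Case | (a) | (b), person-level | Time-varying mediator | Mediator x timepoint |
|---|---|---|---|---|
| Linear, complete | -0.217037 | -0.217037 | -0.009 | -0.009 |
| Linear, 15% missing | -0.25356 | -0.25406 | 0.011 | 0.006 |
| Linear, 30% missing | -0.27840 | -0.27704 | -0.037 | -0.034 |
| Logistic mixed, 15% missing, SD 0.5, mediator 0.5 | -0.3781 | -0.3768 | 0.064 | 0.069 |
| Logistic mixed, 15% missing, SD 1.5, mediator 0.5 | -0.3737 | -0.3754 | 0.032 | 0.059 |
| Ordinary logistic, 15% missing, SD 0.5, mediator 0.25 | -0.2740 | -0.3211 | -0.015 | -0.009 |

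Over 60 trial-size linear datasets (3 or 4 alters per PLWH, complete data), the largest (a)-to-(b) change was 3e-14. Over all six logistic scenarios, the mixed-model coefficient changed by 0.5% or less. The ordinary logistic fit moved 1% to 17%, always away from zero.

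**4. The other quantities, linear complete case.**
- Arm main effect: -0.025 in (a), 0.153 in (b).
- Follow-up contrast: -0.025 - 0.217 = -0.242, then 0.153 - 0.217 = -0.064. The fall is 1 - 0.064/0.242 = 74%, against 75% from step 2.
- Mediator slope: -0.390 in (b) against -0.503 when time-varying, a ratio of 0.78.

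**5. A follow-up-only model.** In a separate simulation, adjusting for baseline outcome and baseline mediator, the arm term went from 0.50 to 0.02 when the post-intervention mediator was added.

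**The case against.** **The coding is not fixed.** The plan never says that the mediator is one value repeated on every row. Mediators are collected at each visit, and the model is fitted to repeated measures, so visit-specific entry is possible. It would work: with an arm-to-mediator effect of 1.0 and a mediator slope of 0.5 (both assumed), a time-varying mediator takes the interaction from 0.499 to -0.005. If baseline rows drop out for want of a post-intervention value, the arm term goes from 0.487 to -0.017. This stands as far as it goes: the rule is not impossible to apply correctly. But time-varying coding is one variable holding both baseline and follow-up values, which fits poorly with adding the two measures in successive steps, and no mediator-by-timepoint term is named.

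**The coefficient is not named in the mediation sentence.** True, and the arm-plus-interaction contrast does fall. It is a sum of two coefficients, however, and it understates mediation (step 2).

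**The bootstrap is a second route.** A reader might infer that Aim 3 is bound to report no mediation whatever the truth. The documents do not support that. The two references cited for the bootstrap have titles about indirect effects, and a product of coefficients would not be zero. If its mediator slope came from model (b), it would be about 75% of the true product. Only a bootstrap of the (a)-to-(b) difference inherits the full fault.

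**Nor can one say flatly that the coefficient cannot change.** That is exact only for linear models with complete data. In the power calculation condomless sex is a proportion, and HIV testing is reported as done or not, so logistic models apply to them. There the coefficient can move, but not in a way that reveals mediation.

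**Conclusion.** The concern holds on the most natural reading: baseline and post-intervention mediators as separate person-level covariates, with the timepoint-by-arm coefficient compared. Under complete mediation the apparent proportion mediated is 0% in a linear model with complete data and within 0.5% of zero in the linear models with missing follow-up and the logistic mixed models simulated. In an ordinary logistic fit it has the wrong sign. The linear complete-data result is algebra and needs no simulation assumption; the other sizes rest on the assumed values in step 3.

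This is more than a missing detail, because the rule, followed in its ordinary sense, gives a wrong answer to a stated aim. It concerns Aim 3 only and leaves the Aim 1 and Aim 2 estimates untouched.

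**What to change.** Either of these serves:

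- Keep the repeated-measures model and let the mediator act by timepoint. Enter it as time-varying (baseline value on baseline rows, visit value on follow-up rows), or cross it with timepoint. Under time-varying coding, (a) becomes the model without the mediator. If crossing is used, cross both the baseline and the post-intervention measure. Change in the outcome is s·(M1 - M0); with only M1 crossed and a baseline-to-post correlation r within arm, the interaction falls only to r·s·d. For r = 0.5 and s·d = 0.25 that is 0.125, so half the effect would still look unmediated.
- Or use follow-up-only models: (a) follow-up outcome on arm, baseline outcome and baseline mediator; (b) the same plus the post-intervention mediator; then compare the arm terms.

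In both cases, name the coefficient compared and the statistic bootstrapped (difference or product). The cost is a few sentences in the analysis plan, with the same data and no change to conduct.

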Aim 4. We will compare *Game Changers* vs. the attention control group in the marginal cost of decreasing alters' condomless intercourse.¹⁴⁶ Using standard methodologies,¹⁴⁶ we define cost-effectiveness ratio (CER) by the difference in per-capita cost of the intervention versus control group divided by the difference in their average effectiveness: $CER = \frac{\mu_{c2} - \mu_{c1}}{\delta_{e2} - \delta_{e1}}$: μ_{c2} is the per-capita cost of *Game Changers*, μ_{c1} is the per-capita cost of the attention control group, δ_{e2} is the percentage of alters reporting any condomless intercourse, and δ_{e1} is the percentage for intervention alters. We will estimate confidence intervals with bootstrap methods.¹⁴⁷ The analysis will be performed from the provider perspective, as we cannot accurately incorporate patient-incurred costs (e.g., given variation in opportunity cost), but we will track the number and length of time spent by patients in intervention and attention control sessions, and assess transportation time and costs. We will use a micro-costing approach recommended by the US Panel on Cost-Effectiveness in Health and Medicine, tracking all costs associated with implementing *Game Changers* and the attention control as estimated from data collected from IDI Finance (e.g., facilitator compensation) and the team.¹⁴⁸ We will collect data using Drummond's checklist of critical elements and follow best practices to maximize comparability of results with other studies.¹⁴⁹ The cost per resource will be calculated by multiplying the quantity used by unit cost; total cost will be derived by adding individual costs.¹⁵⁰ Fixed (capital) costs (e.g., overhead) will be allocated as the hours per week the premises are occupied for the intervention or attention control group. Capital costs will be annualized using a discount rate of 3% with an assumed lifespan of 30 (buildings) and 10 (furniture) years.¹⁵⁰ The analysis will take into account all intervention or attention control group session costs, but exclude costs incurred by participants (e.g., for time) and associated with research. The facilitators will record time spent on the sessions on simple-to-use forms, identifying each activity (e.g., training, preparation, in-session) and session-related materials (e.g., consumable materials). We will differentiate between intervention development (e.g., training) and ongoing costs. Ongoing costs will be tracked to determine any cost efficiencies over time. Within those, we will differentiate between fixed intervention costs and marginal costs of adding a patient, to provide information for generalizability.

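### Aim 3 mediation: for binary outcomes, reading mediation from the drop in a logistic arm coefficient understates partial mediation

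*Combined protocol and SAP*

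**What the plan says.** Specific Aim 3 asks whether "increased HIV prevention advocacy by PLWH mediates intervention effects on their social network members" HIV testing and condom use. Under Statistical Analysis, Aims 1-3, the outcome models are generalized mixed models: "linear for continuous outcomes; logistic for binary outcomes".

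Mediation is examined only if the intervention "shows significant effects on hypothesized mediators (Aim 3), to test mediation we will compare" two models: "a) Aim 1 models, adding baseline measures of mediator(s" and "b) the same models as in (a), adding post-intervention measures of mediator(s". The quantity examined is whether the added mediator "decreases the coefficient for intervention effects on outcomes relative to the corresponding coefficient from (a". A bootstrap test of whether mediators account for effects follows; the section does not say which statistic is bootstrapped.

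HIV testing is collected as whether the alter has been tested (Assessment, Individual-Level Outcomes). Condomless sex is collected as counts, but Statistical Power treats it as a proportion, and Aim 4 defines its effect measure so that it "is the percentage of alters reporting any condomless intercourse". I therefore take both advocacy-pathway outcomes of Aim 3 as yes/no outcomes with logistic models.

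**The concern.** In a linear model, the fall in the arm coefficient when the mediator is added estimates the mediated effect. In a logistic model it does not, because the odds ratio is non-collapsible. Conditioning on a strong predictor of the outcome pushes the arm coefficient away from zero, whether or not the arm changed that predictor. In model (b) this push works against the fall produced by real mediation, so the observed fall is too small. A logistic mixed model has the same property.

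Aim 3 is the trial's test of its mechanism. The advocacy pathway to testing and condom use could be reported as smaller than it is. If the bootstrap is applied to the same difference, the pathway could also be missed more often.

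**Working it through.** **Inputs from the plan.** The plan gives no mediation figure to reproduce. Statistical Power assumes condomless sex at month 18 of 65% (control) and 54.7% (intervention). I use these rates only as a benchmark effect and do not rely on the power attached to them:

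log odds ratio = ln(0.547/0.453) − ln(0.65/0.35) = 0.189 − 0.619 = −0.430.

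The plan's effective sample sizes do reproduce, taking 3.5 × 0.85 = 2.975 alters per PLWH: 625/(1 + 1.975 × 0.01) = 612.9 and 625/(1 + 1.975 × 0.05) = 568.8, against 612 and 568.

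**Assumptions.**
- Arm effect on the mediator, a: 0.2 to 0.4 SD. The pilot gives b = 0.4 for PLWH advocacy, but no SD for the scale.
- Mediator-outcome odds ratio: 1.5 to 2.7 per SD. The plan states none.
- Baseline to follow-up correlation of the mediator: 0.4.
- A single follow-up, independent records and no mediator-outcome confounding.

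**Model.** M1 = 0.4·M0 + a·T + √0.84·e, and logit P(Y) = i + c′·T + b·M1 with b = −ln(OR). The values of i and c′ are solved by quadrature so that the arm rates are exactly 65% and 54.7%. Model (b) recovers c′. Model (a) is the large-sample logistic fit of Y on T and M0, with arm coefficient c.

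- Share read from the rule = 1 − c′/c.
- True share = [P(Y | T=1, mediator as under intervention) − P(Y | T=1, mediator as under control)] / (0.547 − 0.65).

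Example, OR 2 and a = 0.2: the rule gives 1 − 0.337/0.437 = 22.9%. The true share is (0.547 − 0.5778)/(−0.103) = 29.9%.

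| OR per SD | a (SD) | c | c′ | Rule | True | Gap (points) |
|---|---|---|---|---|---|---|
| 1.5 | 0.2 | −0.433 | −0.366 | 15.5% | 18.7% | 3 |
| 1.5 | 0.4 | −0.433 | −0.285 | 34.3% | 37.2% | 3 |
| 2.0 | 0.2 | −0.437 | −0.337 | 22.9% | 29.9% | 7 |
| 2.0 | 0.4 | −0.437 | −0.199 | 54.6% | 59.3% | 5 |
| 2.7 | 0.2 | −0.442 | −0.319 | 27.9% | 39.3% | 11 |
| 2.7 | 0.4 | −0.442 | −0.120 | 72.9% | 77.6% | 5 |

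(Shares come from unrounded coefficients.) A simulation of the OR 2.7, 0.2 SD case gave 28% against 40%, a gap of 12, hence the range of about 3 to 12. At OR 1.25 the gap is about 1 point. If the indirect effect is instead defined by shifting the mediator within the control arm, the gaps in the table's six cases become 1 to 10 points, in the same direction.

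**Where masking would occur.** At OR 2.7 and a = 0.1, the rule shows 5.5% against a true 19.7%. At a = 0 the coefficient grows by 17% with nothing mediated.

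**How often such cases reach the mediation step.** About 178 PLWH are retained (210 × 0.85), so the standard error in SD units is √(4/178) = 0.150, ignoring clustering and baseline adjustment. The smallest significant estimate is 1.96 × 0.150 = 0.29 SD. Power to pass the precondition is about 10% at 0.1 SD and 27% at 0.2 SD. If the mediator were instead analysed per alter (625 records, standard error √(4/625) = 0.08), it is about 24% at 0.1 SD and, since Φ(0.2/0.08 − 1.96) = Φ(0.54), about 71% at 0.2 SD.

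**Full mediation.** If c′ = 0, the rule gives 1 − 0/c = 100%, whatever the scale.

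**Bootstrap.** This was simulated with 612 independent records and no baseline mediator, in 200 trials of 200 resamples each (simulation error about 3 points or more). Power for the coefficient difference against the product of paths was:
- 44.5% against 72% (0.2 SD, OR 2);
- 98.5% against 100% (0.4 SD, OR 2);
- 80.5% against 80.5% (0.4 SD, OR 1.25).

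**The case against.** The best defence has four parts.

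- **The precondition.** Mediation is tested only after a significant arm effect on the mediator. Statistical Power puts detectable differences for PLWH outcomes at .41-.58 SD. At 0.4 SD with odds ratios of 1.25 to 2, the understatement is only about 1 to 5 points.
- **The direction of the comparison usually survives.** In the bootstrap simulations the coefficient still shrank in 94-99% of trials.
- **Shrinkage is not the only criterion.** A bootstrap follows, and the titles of the two papers cited for it concern indirect effects. That is compatible with a product-of-paths statistic, whose test does not depend on comparing the two arm coefficients.
- **No proportion mediated is promised,** so the shares above are a way of expressing the bias, not a planned result.

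Most of this stands, and it limits the point. A reader might infer that the rule will hide a working advocacy pathway, or make a mediator unrelated to arm look like suppression. The documents do not support that: the cases that produce it are largely screened out by the precondition and need a mediator strength that the plan nowhere states. Nor do they support saying that the bootstrap uses the coefficient difference; the statistic is simply unnamed.

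Two things remain. The coefficient comparison is a stated rule, and it is biased in a known direction for logistic models. The precondition also protects less if advocacy is analysed per alter, which the network assessment would allow, because effects near 0.2 SD can then pass.

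**Conclusion.** The point holds as a modest, systematic understatement. For binary Aim 3 outcomes, the drop in the logistic arm coefficient understates partial mediation by about 3 to 12 percentage points when the arm moves the mediator by 0.2 to 0.4 SD and the mediator odds ratio is 1.5 to 2.7 per SD. It is about 1 point for a weak mediator. Near-complete masking is unlikely to reach the mediation step, and full mediation is not hidden. If the bootstrapped statistic is the coefficient difference, it carries the same bias and can lose power when the arm effect on the mediator is modest.

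The direction follows from the stated method. The size rests on assumed mediator strengths, an assumed baseline correlation, the SD reading of the arm effect and the condomless-sex rates. No size is given for HIV testing, because the plan states no month-18 testing rate. Continuous outcomes in linear models are unaffected.

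**What to change.** For binary Aim 3 outcomes, replace the comparison of arm coefficients as follows:

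- Fit a mediator model and an outcome model, both including the baseline mediator.
- By standardisation (g-computation), estimate the natural indirect and direct effects on the risk-difference or risk-ratio scale, stating which natural indirect effect is meant.
- Name that indirect effect as the bootstrapped statistic.
- Resample PLWH together with their alters as the unit.
- Keep the coefficient comparison for continuous outcomes fitted with linear models.

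The cost is a few sentences in the analysis section and modest extra programming; no new data are needed. The method assumes no unmeasured mediator-outcome confounding, as the current approach already does, and the plan should say so.
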